10.3.4. Reporting of SAE to GSK

SAE Reporting to GSK via Electronic Data Collection Tool

• The primary mechanism for reporting SAE to GSK will be the electronic data collection tool.• If the electronic system is unavailable, then the site will use the paper SAE data collection tool (see next section) in order to report the event within 24 hours.• The site will enter the SAE data into the electronic system as soon as it becomes available.• The investigator or medically-qualified sub-investigator must show evidence within the eCRF (e.g., check review box, signature, etc.) of review and verification of the relationship of each SAE to IP/study participation (causality) within 72 hours of SAE entry into the eCRF.• After the study is completed at a given site, the electronic data collection tool will be taken off-line to prevent the entry of new data or changes to existing data.• If a site receives a report of a new SAE from a study participant or receives updated data on a previously reported SAE after the electronic data collection tool has been taken off-line, then the site can report this information on a paper SAE form (see next section) or to the medical monitor by telephone.• Contacts for SAE reporting can be found in the study reference manual (SRM).

SAE Reporting to GSK via Paper CRF

• Facsimile transmission of the SAE paper CRF is the preferred method to transmit this information to the medical monitor if the electronic data collection tool described above is not available.• In rare circumstances and in the absence of facsimile equipment, notification by telephone is acceptable with a copy of the SAE data collection tool sent by overnight mail or courier service.• Initial notification via telephone does not replace the need for the investigator to complete and sign the SAE CRF pages within the designated reporting time frames.• Contacts for SAE reporting can be found in SRM.

10.4. Appendix 4: Contraceptive Guidance and Collection of Pregnancy Information

10.4.1. Definitions:

Woman of Childbearing Potential (WOCBP)

A woman is considered fertile following menarche and until becoming post-menopausal unless permanently sterile (see below).

If fertility is unclear (e.g., amenorrhea in adolescents or athletes) and a menstrual cycle cannot be confirmed before first dose of study intervention, additional evaluation should be considered.

Women in the following categories are not considered WOCBP

1. Premenarchal
2. Premenopausal female with 1 of the following:
 - Documented hysterectomy
 - Documented bilateral salpingectomy
 - Documented bilateral oophorectomy

For individuals with permanent infertility due to an alternate medical cause other than the above, (e.g., mullerian agenesis, androgen insensitivity), investigator discretion should be applied to determining study entry.

Note: Documentation can come from the site personnel's: review of the participant's medical records, medical examination, or medical history interview.

3. Postmenopausal female
 - A postmenopausal state is defined as no menses for 12 months without an alternative medical cause.
 - A high follicle stimulating hormone (FSH) level in the postmenopausal range may be used to confirm a postmenopausal state in women not using hormonal contraception or hormonal replacement therapy (HRT). However, in the absence of 12 months of amenorrhea, confirmation with more than one FSH measurement is required.
 - Females whose menopausal status is in doubt will be required to use one of the non- hormonal highly effective contraception methods.

10.4.2. Contraception Guidance:

Female participants of childbearing potential that are not currently utilizing a highly-effective contraceptive method (non-hormonal) are eligible to participate if a pregnancy test conducted during screening and again pre-dose (Day -1) is negative. It is not

necessary to require participants to start a new contraceptive method if they are not already established on one.

Female participants of childbearing potential that are currently utilizing a highly-effective contraceptive method are eligible to participate if they agree to continue to use this method consistently and correctly as described below. In this instance a negative pregnancy test during screening and again pre-dose (Day -1) would not be required.

CONTRACEPTIVES^a ALLOWED DURING THE STUDY INCLUDE:	
Highly Effective Methods^b That Have Low User Dependency Failure rate of <1% per year when used consistently and correctly.	
Intrauterine device (IUD)	
Bilateral tubal occlusion	
Vasectomized partner Note: Vasectomized partner is a highly effective contraceptive method provided that the partner is the sole sexual partner of the woman of childbearing potential and the absence of sperm has been confirmed. If not, an additional highly effective method of contraception should be used. Spermatogenesis cycle is approximately 90 days.	
Highly Effective Methods^b That Are User Dependent Failure rate of <1% per year when used consistently and correctly.	
Sexual abstinence Note: Sexual abstinence is considered a highly effective method only if defined as refraining from heterosexual intercourse during the entire period of risk associated with the study intervention. The reliability of sexual abstinence needs to be evaluated in relation to the duration of the study and the preferred and usual lifestyle of the participant.	
ACCEPTABLE METHODS^c	
Male or female condom with or without spermicide ^d	
Cervical cap, diaphragm, or sponge with spermicide	
A combination of male condom with either cervical cap, diaphragm, or sponge with spermicide (double-barrier methods) ^c	

 a. Contraceptive use by men or women should be consistent with local regulations regarding the use of contraceptive methods for those participating in clinical studies. b. Failure rate of <1% per year when used consistently and correctly. Typical use failure rates differ from those when used consistently and correctly. c. Considered effective, but not highly effective - failure rate of $\geq 1\%$ per year. Periodic abstinence (calendar, sympto-thermal, post-ovulation methods), withdrawal (coitus interruptus), spermicides only, and lactational amenorrhoea method (LAM) are not acceptable methods of contraception. d. Male condom and female condom should not be used together (due to risk of failure with friction). 	

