1.3. Schedule of Activities (SoA)

Part A -OR- Part B

Procedure	Screen ¹	Intervention (Part A Periods 1, 2, & 3 OR Part B Periods 1 & 2) ¹⁰												Follow-up ⁹
		Day -1	Pre-dose	0h	0.5h	1h	2h	2.5h	3h	4h	6h	8h	12h	
Informed Consent	X													
Inclusion / Exclusion ²	X	X												
Demography	X													
Physical Examination ³	X	X												
12-Lead electrocardiogram (ECG)	X													
Vital Signs ⁴	X	X	X											X
Clinical Laboratory Test ⁵	X	X												X
Pregnancy Test ⁶	X	X												X
Urine Drug Screen and Alcohol Screen ⁷	X													
Randomization		X												
Study Intervention Dose ⁸				X										
PK Blood Sampling			X		X	X	X	X	X	X	X	X	X	
AE/Serious AE		←-----→												
Concomitant Medication Review		←-----→												
Admission to Unit		X												
Discharge from Unit														X
Outpatient Visit	X													X
COVID-19 testing (PCR or antigen)	X	X ¹²		<-----Ad hoc based on continuous review----->										

¹Within 30 days of Day 1, Period 1

²Re-check eligibility at Day -1 (admission to Unit)

³Brief Physical Examination on Day -1

⁴Body temperature, pulse, systolic & diastolic blood pressure (semi-supine)

⁵ Hematology, clinical chemistry (including liver), and urinalysis

⁶ Urine or serum per site standard; females only

⁷ Alcohol screening can be performed via urine or breathalyser per site standard

⁸ Time 0 is the time of study interventional drug dosing, and all subsequent timed assessments are calculated from Time 0.

⁹ 7 (± 1) days from dose day Period 3, Part A -OR- 7 (± 1) days from dose day Period 2, Part B. Same assessments will be performed for early withdraw visit.

¹⁰ A minimum of 7 days is required between each treatment-period's dosing, i.e., at least 7 days between Period 1 and Period 2, and between Period 2 and Period 3 dosing in Part A, and 7 days between Period 1 and Period 2 dosing in Part B

¹² COVID-19 PCR or antigen testing may be done prior to Day -1 (admission to the study unit) such that the results are timed to arrive just prior to admission, ideally within 72h of admission to the study unit.

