5.1. Inclusion Criteria

Participants are eligible to be included in the study only if all the following criteria apply:

Age

1. Participant must be 18 to 50 years of age inclusive, at the time of signing the informed consent.

Type of Participant and Disease Characteristics

2. Participants must be overtly healthy as determined by medical evaluation including medical history, physical examination, and laboratory tests. A participant with a clinical abnormality or laboratory parameter(s) which is/are not specifically listed in the inclusion or exclusion criteria, outside the reference range for the population being studied may be included only if the investigator and/or the Medical Monitor agree and document that the finding is unlikely to introduce additional risk factors and will not interfere with the study procedures

Weight

3. Body weight \geq 45 kg and body mass index (BMI) within the range 19-31 kg/m² (inclusive).

Sex

4. Male or female

Female participants: A female participant is eligible to participate if she is not breastfeeding, and at least one of the following applies (see [Appendix 4](#)):

- (i) Not pregnant as confirmed by pregnancy testing
- (ii) Not a woman of childbearing potential (WOCBP)
- (iii) For WOCBP that are currently utilizing a highly-effective contraceptive method prior to enrolment, agrees to follow the contraceptive guidance during the treatment period to the follow-up visit.

Informed Consent

5. Capable of giving signed informed consent as described in [Appendix 1](#) which includes compliance with the requirements and restrictions listed in the informed consent form (ICF) and in this protocol.

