5.4. Screen Failures

Screen failures are defined as participants who consent to participate in the clinical study but are not subsequently randomized. A minimal set of screen failure information is required to ensure transparent reporting of screen failure participants to meet the Consolidated Standards of Reporting Trials (CONSORT) publishing requirements and to respond to queries from regulatory authorities. Minimal information includes demography, screen failure details, eligibility criteria, any protocol deviations and any serious adverse events (SAEs).

Individuals who do not meet the criteria for participation in this study (screen failure) may be rescreened participant to consultation with the GSK Medical Monitor. In the case of a re-screen, the participant should be assigned a new participant number.

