8.2.1. Time Period and Frequency for Collecting AE and SAE Information

- All SAEs will be collected from the start of intervention until the follow-up visit at the time points specified in the SoA (Section [1.3](#)). However, any SAEs assessed as related to study participation (e.g., study intervention, protocol-mandated procedures, invasive tests, or change in existing therapy) or related to a GSK product will be recorded from the time a participant consents to participate in the study.
- All AEs will be collected from the start of intervention until the follow-up visit at the time points specified in the SoA (Section [1.3](#)).
- Medical occurrences that begin before the start of study intervention but after obtaining informed consent will be recorded on the Medical History/Current

Medical Conditions section of the CRF not the AE section unless they are assessed as related to study participation.

- All SAEs will be recorded and reported to the sponsor or designee immediately and under no circumstance should this exceed 24 hours, as indicated in [Appendix 3](#). The investigator will submit any updated SAE data to the sponsor within 24 hours of it being available.
- Investigators are not obligated to actively seek AEs or SAEs after the conclusion of the study participation. However, if the investigator learns of any SAE, including a death, at any time after a participant has been discharged from the study, and he/she considers the event to be reasonably related to the study intervention or study participation, the investigator must promptly notify the sponsor.

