10.2. Appendix 2: Clinical Laboratory Tests

- The tests detailed in [Table 2](#) will be performed by the local laboratory.
- Protocol-specific requirements for inclusion or exclusion of participants are detailed in [Section 5](#) of the protocol.
- Additional tests may be performed at any time during the study as determined necessary by the investigator or required by local regulations.
- Pregnancy Testing
 - Refer to [Section 5.1](#) Inclusion Criteria for screening pregnancy criteria.
- Pregnancy testing (urine or serum as required by local regulations) should be conducted at screening, Day (-1), and at the follow up visit during study.
- Pregnancy testing (urine or serum as required by local regulations) should be conducted at the end of relevant systemic exposure.
- Additional serum or urine pregnancy tests may be performed, as determined necessary by the investigator or required by local regulation, to establish the absence of pregnancy at any time during the participant's participation in the study.

Table 2 Protocol-Required Safety Laboratory Assessments

Laboratory Assessments	Parameters			
Hematology	Platelet Count	RBC Indices: Mean corpuscular volume (MCV) Mean corpuscular Hgb (MCH) %Reticulocytes	White blood cells (WBC) count with Differential: Neutrophils Lymphocytes Monocytes Eosinophils Basophils	
	Red blood cells (RBC) Count			
	Hemoglobin			
	Hematocrit			
Clinical Chemistry ¹	Blood Urea Nitrogen (BUN)	Potassium	Aspartate Aminotransferase (AST)/ Serum Glutamic-Oxaloacetic Transaminase (SGOT)	Total and direct bilirubin
	Creatinine	Sodium	Alanine Aminotransferase (ALT)/ Serum Glutamic-Pyruvic Transaminase (SGPT)	Total Protein

Laboratory Assessments	Parameters			
	Glucose fasting	Calcium	Alkaline phosphatase	
Routine Urinalysis	
 Specific gravity pH, glucose, protein, blood, ketones, bilirubin, urobilinogen, nitrite, leukocyte esterase by dipstick Microscopic examination (if blood or protein is abnormal) 			

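### Inclusion 4 and Appendix 4 together leave no explicit bar to dosing a woman who is already pregnant at consent if she uses a highly effective contraceptive method

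*Protocol*

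**What the plan says.** Inclusion 4 (Protocol Section 5.1) opens for women with: "A female participant is eligible to participate if she is not breastfeeding, and at least one of the following applies". Three items follow:

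- (i) a pregnancy test confirms she is not pregnant;
- (ii) she is not a WOCBP;
- (iii) "For WOCBP that are currently utilizing a highly-effective contraceptive method prior to enrolment, agrees to follow the contraceptive guidance", through to the follow-up visit.

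Appendix 4 (Section 10.4.2) divides WOCBP by contraceptive status. Those not on a highly effective method are "eligible to participate if a pregnancy test conducted during screening and again pre-dose (Day -1) is negative". Those already on one are eligible if they agree to continue it properly, and for them the text adds: "In this instance a negative pregnancy test during screening and again pre-dose (Day -1) would not be required".

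The Schedule of Activities (Section 1.3) places a pregnancy test at screening, Day -1 and follow-up, with the footnote "Urine or serum per site standard; females only". Appendix 2 (Section 10.2) says that pregnancy testing "should be conducted at screening, Day (-1), and at the follow up visit during study", and refers back to Section 5.1 for the pregnancy criteria at screening. The exclusion criteria (Section 5.2) do not mention pregnancy.

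Once a woman is in the study, the position is clear. Section 7.1.2 permanently stops dosing in a participant who becomes pregnant, and Section 10.4.3 withdraws her.

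**The concern.** The protocol evidently does not intend to dose pregnant women, since pregnancy during the study ends both dosing and participation. At entry, however, breastfeeding is an unconditional bar and pregnancy is not. For WOCBP on a highly effective method, a statement about contraception takes the place of a negative test. Current contraception does not show that she was not pregnant when she consented.

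The test that would detect such a pregnancy is already scheduled, but nothing says what a positive result means for this group. Participants gain no benefit from the drug (Section 2.3.1), so there is no counterweight to an avoidable exposure. The documents give no embryo-fetal risk data, and no harm is claimed here. What is at stake is an explicit entry safeguard for participants; the statistical analysis is not affected.

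**Working it through.** The protocol gives no figure on this point to reproduce, so the check is of eligibility logic.

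**Test case.** A WOCBP who is pregnant at consent, is not breastfeeding, has an intrauterine device (listed as highly effective in Appendix 4) and agrees to continue with it.

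**Step 1: Inclusion 4.** The rule is: not breastfeeding AND [(i) OR (ii) OR (iii)].

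- Not breastfeeding: true
- (i) not pregnant by test: false
- (ii) not a WOCBP: false
- (iii) on a highly effective method and agrees to the guidance: true

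True AND (false OR false OR true) = true, so Inclusion 4 is met.

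**Step 2: Appendix 4.** The negative-test condition applies only to WOCBP not on a highly effective method. For the test case it is expressly waived.

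**Step 3: exclusions.** The number of criteria in Section 5.2 that name pregnancy is 0.

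**Step 4: does another provision supply the bar?**

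- Schedule of Activities: schedules the test and an eligibility re-check at Day -1, but attaches no consequence to the result.
- Appendix 2: schedules the test, then refers back to Section 5.1, which is the criterion in question.
- Sections 7.1.2 and 10.4.3: address a participant who becomes pregnant, not one who enters pregnant.
- The ban on protocol waivers (Sections 5 and 8): does not help, because on the literal wording she needs no waiver.

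**Step 5: limits of the gap.** Conception after consent is covered. People who have consented already count as participants: Section 5.4 states "Screen failures are defined as participants who consent to participate in the clinical study but are not subsequently randomized", and Section 8.2.1 says study-related serious adverse events "will be recorded from the time a participant consents to participate in the study". Section 10.4.3 therefore applies from consent, and Section 7.1.2 also applies once dosing has begun. What remains is essentially pregnancy already present at entry.

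**Step 6: size.** The documents give neither the share of participants who are WOCBP on a highly effective method nor the frequency of pregnancy at entry, so no count can be derived. Maximum total dose, if such a woman completed every period:

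- Part A: 3 × 4 mg = 12 mg
- Part B: from 2 × 1 mg = 2 mg (lowest strength) to 2 × 8 mg = 16 mg (highest strength)

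**The case against.** The strongest reply is that this is a drafting slip that existing controls would catch.

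- **Reading of the waiver.** Appendix 4 says that eligibility need not depend on a negative test. It does not say that a known positive is acceptable. This is the more natural reading, and it stands.
- **General controls.** Females are tested at screening and Day -1, and eligibility is re-checked on Day -1. Inclusion 2 requires good health on medical evaluation, including laboratory tests, and allows an unlisted abnormality only with a documented judgement that it is unlikely to add risk. Section 7.2 lets the investigator withdraw a participant for safety, and Section 8 sends immediate safety concerns to the sponsor. Together these make dosing after a known positive unlikely. They all rest on judgement, however, and none names pregnancy as a bar.
- **Narrow group.** The highly effective methods in Appendix 4 are the intrauterine device, tubal occlusion, a vasectomized partner and abstinence, each with a failure rate below 1% per year when used consistently and correctly. For abstinence, and often for a vasectomized partner, a pregnancy would itself call into question whether item (iii) applies. This makes the case rarer, but it does not remove it for an intrauterine device or tubal occlusion.
- **Consent form.** Inclusion 5 makes compliance with the consent form's restrictions part of eligibility, and that form is not among the documents reviewed. It may contain a bar, but this cannot be assumed, and the protocol's own criteria should be correct without it.
- **Sponsor's choice.** Linking the test condition to contraceptive status appears deliberate, and one exclusion line would close the literal gap. That is a fair argument for the shorter remedy. Leaving the waiver sentence beside such a line would still give sites conflicting guidance.

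**Conclusion.** The concern holds. As worded, the eligibility rule accepts a WOCBP who is pregnant at consent and uses a highly effective method; her negative test is waived and no exclusion names pregnancy. The conclusion rests on the protocol text alone and assumes that the consent form does not add a bar.

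Severity is minor. The scope is limited to pregnancy present at entry, the frequency cannot be estimated, no harm is claimed, and scheduled testing with investigator judgement makes dosing after a known positive unlikely. Maximum exposure would be 12 mg in Part A and 2 to 16 mg in Part B, depending on strength. Confidence in the reading of the text is high.

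**What to change.** 1. Delete the Appendix 4 sentence that waives the negative screening and Day -1 tests.
2. Reword Inclusion 4 so that every WOCBP must have a negative test at screening and at Day -1 of Period 1, with the contraceptive guidance as an additional condition for those already on a highly effective method. Alternatively, add a positive pregnancy test to the exclusion criteria in Section 5.2.
3. State that a positive Day -1 test bars dosing.

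The pregnancy-test footnote in the Schedule of Activities can stay as it is.

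The cost is a few lines in a protocol amendment, which needs IRB/IEC approval under Section 10.1.1. No test or visit is added, because Sections 1.3 and 10.2 already schedule the testing. The SAP needs no change.

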10.4.3. Collection of Pregnancy Information:**Female Participants who become pregnant**

- Investigator will collect pregnancy information on any female participant, who becomes pregnant while participating in this study.
- The initial information will be recorded on the appropriate form and submitted to GSK within 24 hours of learning of a participant's pregnancy.
- Participant will be followed to determine the outcome of the pregnancy. The investigator will collect follow up information on participant and neonate, which will be forwarded to GSK. Generally, follow-up will not be required for longer than 6 to 8 weeks beyond the estimated delivery date.
- Any termination of pregnancy will be reported, regardless of fetal status (presence or absence of anomalies) or indication for procedure.
- While pregnancy itself is not considered to be an AE or SAE, any pregnancy complication or elective termination of a pregnancy for medical reasons will be reported as an AE or SAE.
- A spontaneous abortion (occurring at < 22 weeks gestational age) or still birth (occurring at > 22 weeks gestational age) is always considered to be an SAE and will be reported as such.
- Any SAE occurring as a result of a post-study pregnancy which is considered reasonably related to the study intervention by the investigator, will be reported to GSK as described in [Appendix 3](#). While the investigator is not obligated to actively seek this information in former study participants, he or she may learn of an SAE through spontaneous reporting.

Any female participant who becomes pregnant while participating

- will be withdrawn from the study

